Non-operative management of splenic and hepatic injuries has become one of the standards of care in the management of hemodynamically stable patients. Institutional variance exists in management of these injuries regarding serial laboratory values, transfusion thresholds, the utility of interventional radiology/operative management, follow up imaging, and management of delayed findings on this imaging. The delayed complications found both clinically and with follow up imaging vary in the literature from nearly 0% to >15% of cases. There is no clear evidence as to the necessity of repeat imaging or frequency of intervention in blunt splenic and hepatic injuries. Some studies recommend only follow up

imaging for high grade injuries, whereas other studies have found no correlation between grade of injury and complications.

Our group approached this question through a dual institution, retrospective pilot study observing the management of delayed splenic and hepatic complications found on repeat imaging. This study was performed in the adult population and a current study is ongoing in the pediatric population. Imaging was obtained either via the institutions standard protocol (SP) or physician discretion (PD) (lab or vital sign abnormalities, clinical change, etc). There were 235 splenic injuries with 45% undergoing repeat imaging. 64% of these were due to PD. Complications were found in 47% of SP and 42% of PD patients (p=0.683). Interventions performed for these complications was done for 56% SP v. 21% of PD patients (p=0.027). This pilot study suggested that patients with blunt splenic injuries should undergo repeat imaging for delayed complications and that those who underwent repeat imaging by SP had complications identified sooner (2.4 v 4.4 days) and treated earlier than the PD group.

Of the 365 liver injuries, 33.4% underwent repeat imaging with a majority (59%) of these due to physician discretion. Complications were found in 20% of SP patients and 27% of PD patients (p=0.395). Interventions were performed in 20% SP v. 25% PD patients that had complications (p=1.00). In the liver injury group there was no difference found between complications or interventions performed when assessed by SP or PD; waiting to perform repeat imaging based on PD could prevent unnecessary imaging in blunt liver injuries.

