In this small pilot study we were unable to achieve all of our primary and secondary endpoints. Additionally, interventions in low grade injuries are uncommon, and a larger data set would allow for delineation in management between low, moderate and high grade splenic and hepatic injuries. This study did not have power due to a limited number of patients receiving interventions, thus making characterization of types of interventions and final outcomes difficult.

A large multicenter trial would allow for appropriate power for the study and thus allow for us to meet our endpoints. There are multiple variables affecting the management of blunt splenic and hepatic injuries and currently no clear guidelines exist in regards to repeat imaging. Gaining a better understanding of types of delayed complications, how they present, and current management strategies would assist in creating a standardized algorithm in the treatment of this patient population.

Specific Aims of Multicenter Study

Aim 1: To define which blunt splenic and hepatic injuries are at risk of delayed complications in order to develop a societal management guideline.

Aim 2: To ascertain which patients warrant repeat imaging and when this imaging should be performed.

Aim 3: To define what interventions are needed based upon delayed complications found radiographically.

Aim 4: To analyze 30 day readmission rates to the hospital due to spleen and/or liver injury.

Methods

This will be a retrospective observational study. Patients will be managed according to the surgeon's discretion. The study will enroll a total of 5,000 subjects at minimum. This study plans to enroll 200 patients at our institution, Penn Medicine Lancaster General Health. The number of subjects that will be enrolled at each additional participating site is 200.

Inclusion Criteria:

• All patients (all ages) who present with blunt trauma to the spleen and/ or liver

Exclusion Criteria:

- Patients who suffer a penetrating mechanism
- Patients transferred out to another facility prior to admission

Updated Terms/Definitions:

• **Clinical Change (CC) (to replace Physician Discretion)**- repeat imaging prompted by patient factors including vital sign changes, lab abnormalities, abdominal pain, and patient symptoms

• Non Clinical Change (NCC) (to replace Standard Protocol)- repeat imaging prompted by institutional protocol/ recommendations, individual physician practice pattern, or that performed on a scheduled basis

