The time frame for data query will be from IRB approval (2020) until December 31, 2023. The electronic medical record (EMR) may be used in order to identify participants who match study defined demographic criteria.

Primary Outcome: Delayed complications found on repeat imaging

Secondary Outcomes: Timing to repeat imaging/ intervention, interventions performed based on complications found, mortality, length of stay, blood transfusion requirements, VTE prophylaxis, and 30 day readmission variables [readmission within 30 days for spleen and/or liver injury, readmission CT scan, interventions performed].

Variables

List specific variables to be collected & analyzed: Age, sex, time from injury, Injury Severity Score (ISS), Abbreviated Injury Scale (AIS), Trauma and Injury Severity Score (TRISS), mechanism of injury, initial vital signs, anticoagulant use and reversal agents, initial and repeat imaging, grade of organs injured, complications found, details regarding initial and any delayed interventions, blood transfusions, details regarding venous thromboembolism prophylaxis, venous thromboembolism complications, hospital length of stay, intensive care unit length of stay, mortality, and 30 day readmission variables [readmission within 30 days for spleen and/or liver injury, readmission CT scan, interventions performed].

Data Collection and Statistical Analysis

Standardized data will be collected for each patient meeting inclusion criteria (see data collection tool). The de-identified data for each patient will be entered into a secure REDCap database. A total of 5,000 patients (3,500 splenic injuries and 1,500

hepatic injuries) is recommended to identify a significant difference between the non clinical change and clinical change group. Complications found on repeat imaging will be assessed using univariate and multivariate analysis.

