First Repeat Imaging Hours from Admission	If yes checked for First Repeat Imaging, numerical value for when repeatimaging was performed in hours from admission.
Reason for First Repeat Imaging	If yes checked for First Repeat Imaging, single choice for best reason for scan. Options include:
	Clinical Change: Repeat imaging prompted by patient factors including, but not limited to, vital sign changes, lab abnormalities, abdominal pain, and patient symptoms.
	Non-Clinical Change: Repeat imaging prompted by institutional protocol/recommendations, individual physician practice pattern, or that performed on a scheduled basis.
First Repeat Imaging Findings	If yes checked for First Repeat Imaging, free text of organ specific (hepatic or splenic) imaging findings.
Organ Specific Delayed Complication	tions
Liver Complications	Liver specific complications found during hospital admission. Check all that apply. Options include:
	Increased bleeding, including increased hemoperitoneum. Pseudoaneurysm Hemobilia New area of hepatic injury not previously recognized on initial workup. Hepatic infarct (not post-IR/post-intervention). Abscess Fulminant liver failure Bile leak/biloma Unexpected thrombosis (of hepatic and related vessels) Need for OR/intervention other than initial Other (free text)

Organ Specific Delayed Complications (continued)

Spleen Complications	Spleen specific complications found during hospital admission. Check all that apply. Options include:
	Increased bleeding, including increased hemoperitoneum. Pseudoaneurysm Delayed rupture. New area of splenic injury not previously recognized on initial workup. Splenic infarct (not post-IR/post-intervention). Abscess Unexpected thrombosis (of splenic and related vessels) Pancreatic fistula Arteriovenous fistula Need for OR/intervention other than initial Other (free text)
Intervention Information	
Initial Intervention	Intervention for hepatic and/or splenic injury prior to repeat imaging (can occur post-initial imaging assessment). Yes/No dropdown menu. Yes = intervention performed for hepatic and/or splenic injury at initial assessment, prior to repeat imaging. No = no intervention performed for hepatic and/or splenic injury at initial assessment, prior to repeat imaging.
Initial Intervention Timing	If yes checked for Initial Intervention, numerical value for time to intervention from presentation (in hours).

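### Complications visible only on imaging can be found only in scanned patients, and neither the risk model nor the scan-reason code deals with who was scanned

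*Supplement*

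**What the plan says.** The protocol's Methods admit "All patients (all ages) who present with blunt trauma to the spleen and/ or liver", excluding only penetrating mechanisms and transfers out before admission. Care, and so the decision to scan again, rests with the surgeon. The outcome line reads "Primary Outcome: Delayed complications found on repeat imaging". Aim 1 seeks the injuries at risk, to support a guideline; the next is "Aim 2: To ascertain which patients warrant repeat imaging and when this imaging should be performed".

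The section Data Collection and Statistical Analysis plans a mixed-effects logistic model with a binary delayed-complication outcome. It does not say whether the model takes all injured patients or only those scanned, and it describes no adjustment for being scanned.

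In the pilot, "Imaging was obtained either via the institutions standard protocol (SP) or physician discretion (PD") were the two routes to a scan. The current protocol renames them, with "Non Clinical Change (NCC) (to replace Standard Protocol") as one of the two new groups. The Data Dictionary, under Reason for First Repeat Imaging, defines that group as "Repeat imaging prompted by institutional protocol/recommendations, individual physician practice pattern, or that performed on a scheduled basis". The field is "If yes checked for First Repeat Imaging, single choice for best reason for scan", with two options: clinical change and non-clinical change.

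The dictionary's liver and spleen complication fields cover anything found during the admission. Unlike the repeat-imaging fields, they do not depend on a repeat scan having been done.

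**The concern.** Aims 1 and 2 ask about risk in injured patients. A complication that shows only on imaging, such as a silent pseudoaneurysm, cannot be detected in a patient who is not scanned again. The observed complication rate therefore mixes two things: how often complications occur and how often anyone looked.

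The two obvious ways to run the model both carry this mixture. Entering unscanned patients as complication-free turns determinants of scanning into apparent determinants of risk. Leaving them out gives risk among patients whom someone decided to scan, often because of suspicion. The Background reports that studies disagree on whether injury grade predicts complications. Grade could well influence scanning, so this bias bears on the very question the study hopes to settle, and a larger sample does not remove it.

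The reason code matters because scans done by rule or schedule are the natural check on this bias. One code that merges them with an individual physician's habits makes that check impossible from the field as it stands.

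**Working it through.** **1. The plan's own figures.** Inputs are the rates in Sample Size and Power Estimates: spleen 0.47 v 0.42, liver 0.20 v 0.27. With p̄ the mean of the two rates, the size per group is n = [1.960·√(2p̄(1−p̄)) + 0.842·√(p1(1−p1)+p2(1−p2))]² / (p1−p2)².

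- Spleen: n = 1,550, total 3,100.
- Liver: n = 575, total 1,150.

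Both match the tables, as do the other four rows. Two-sided 5%, 80% power and 1:1 allocation are inferred from the match, apart from the stated 0.05 level. The rates are 18/38 and 28/67 (spleen), 10/50 and 20/72 (liver). Their denominators are scanned patients: 38 + 67 = 105 and 50 + 72 = 122.

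**2. How many were unscanned.** Spleen: 235 − 105 = 130 (55%). Liver: 365 − 122 = 243 (67%). At the same scan rates, 3,500 splenic injuries give 3,500 × 105/235 ≈ 1,564 scanned and 1,936 unscanned. For 1,500 hepatic injuries it is 1,500 × 122/365 ≈ 501 scanned and 999 unscanned.

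**3. Risk by denominator.** The pilot's complications are all accounted for by its two scanned groups (18 + 28 = 46; 10 + 20 = 30).

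| | Among scanned | Among all injured | Upper bound if every unscanned patient had one |
|---|---|---|---|
| Spleen | 46/105 = 43.8% | 46/235 = 19.6% | (46+130)/235 = 74.9% |
| Liver | 30/122 = 24.6% | 30/365 = 8.2% | (30+243)/365 = 74.8% |

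The last column is a logical limit, not a plausible estimate.

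**4. Unscanned counted as zero.** Assume two grades with the same true risk of 30%, scanning unrelated to complication within grade, and no detection without a scan. The scan rates are also assumed.

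- Scanned 25% v 65%: observed 0.30 × 0.25 = 7.5% v 0.30 × 0.65 = 19.5%; OR = (0.195/0.805)/(0.075/0.925) = 2.99.
- Scanned 35% v 55%: observed 10.5% v 16.5%; OR = (0.165/0.835)/(0.105/0.895) = 1.68.

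The true odds ratio is 1.0 in both.

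**5. Unscanned dropped.** Under the same assumptions the scanned-only comparison is 30% v 30%, OR 1.0. That relies on scanning being unrelated to complication within grade. Clinical-change scans are by definition prompted by the patient's condition, so it is doubtful for them. The documents give no figure from which to size this bias.

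**6. The reason field.** The pilot kept institutional protocol apart from physician discretion. The current non-clinical-change group holds three triggers: institutional protocol, individual practice pattern and schedule. With one two-option field, these cannot be told apart. If protocol scans could be isolated and occurred at pilot rates, they would number 3,500 × 38/235 ≈ 566 splenic and 1,500 × 50/365 ≈ 205 hepatic.

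**The case against.** Several points on the other side are good.

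- **Outcome.** A reader might infer that an unscanned patient cannot have the outcome at all. That fits the primary outcome line but not the dictionary, whose complication fields are open to everyone and list items that can be recorded without a scan, such as delayed rupture or need for a further intervention. Readmission for the injury is also captured. What stands is narrower: imaging-only findings are missed in unscanned patients, and the two definitions disagree.
- **Scan reason.** It is tempting to say that protocol scans alone are unselected. No site protocol is shown, the Background notes that some studies advise follow-up imaging only for high-grade injury, and a protocol may follow that. Scheduled scans may be equally unselected. Practice pattern may mean a routine rather than a choice for one patient. The pilot's discretion arm was itself described by laboratory, vital-sign and clinical triggers, so the new split may separate patient-triggered from routine scans better than the old one. Nor are the triggers beyond recovery, since charts and site identifiers exist. What stands is that this field cannot separate them.
- **Pilot split.** A reader might infer that the pilot's 38:67 allocation underlies the sample size. It does not; the tables reproduce at 1:1.
- **Analysis set.** The power denominators suggest that scanned patients are meant, which would avoid the zero-coding bias. That is an inference from another section, and it leaves the conditioning on being scanned. A fuller analysis plan might settle it, but the outcome definition and the reason code belong to the protocol and dictionary.

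**Conclusion.** The concern holds in this form: for imaging-only complications, outcome status is unknown in unscanned patients, who were more than half of the pilot, and the plan does not address it for the aims that depend on it. The choice of denominator alone moves splenic risk between 43.8% and 19.6% and hepatic risk between 24.6% and 8.2%. Zero-coding can create an odds ratio of about 1.7 to 3.0 from no true difference, under the assumed scan rates and no clinical detection. For the scanned-only route the direction and size of bias cannot be derived from the documents. The projections assume that the adult, two-institution pilot's scan rates carry over to a multicentre study of all ages. The reason-code point is secondary: it removes a useful check but does not cause the bias.

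**What to change.** 1. Reconcile the primary outcome line with the dictionary's complication fields. Do not code imaging-only complications as absent in never-scanned patients; treat them as unknown. Keep complications recorded clinically without a scan.
2. For Aims 1 and 2, fit the risk model in scanned patients with inverse-probability weighting for being scanned, using grade, ISS, initial vital signs, anticoagulation and site, all already collected. Show it beside the unweighted model. These are mainly admission variables, so weighting cannot fully correct for scans triggered by later deterioration; say so.
3. Split the reason field into clinical change, institutional protocol or scheduled, and individual physician practice, with the same wording on the collection form. Report the risk model in protocol or scheduled scans as a sensitivity analysis. It omits patients whose first scan followed an earlier clinical change, so it complements the weighted model rather than replacing it.
4. Describe the clinical versus non-clinical contrast as scan yield, not underlying risk.

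The cost is one more code, a few sentences on analysis sets, wider intervals (about 566 splenic and 205 hepatic in the sensitivity analysis if limited to protocol scans), and re-abstraction of the reason field for any records already entered.

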east	Eastern Association for the Surgery of Trauma Advancing Science, Fostering Relationships, and Building Careers
	EAST MULTICENTER STUDY DATA COLLECTION TOOL
Multicenter Study:	
Enrolling Center: Enrolling Co-investigator:	
Demographic Variables	
Age: Sex:	Weight (kg):
Description of Initial Injury	
Estimated time from injury to pro	esentation (in hours):
ISS: AIS Head/Neck	:: AIS Face: AIS Chest:
AIS Abdomen/Pelvis:	AIS Extremity: AIS External:
TRISS:	
Bicycle Pedest Assault Crush I Motorc Non-ac Sports Other/U	/ehicle Crash rian Struck t (by person or animal) njury ycle Crash/All-Terrain Vehicle (ATV) Crash ccidental Trauma (NAT)
Vital Signs on Presentation	
SBP: HR:	SpO2: GCS:
Admission Anticoagulation a	nd Reversal:
	tiplatelet therapy (defined as a patient home medication or present at time of

Admission Anticoagulation and Reversal (continued)
--

Anticoagulation/Antiplatelet agent (cheo Warfarin Apixaban Aspirin Ticagrelor	ck all tha	it are pr	esent at	time of i	initial trauma assessment): Rivaroxaban Dabigatran Clopidogrel Other
Reversal agents given (defined as a re- initial trauma assessment) (Circle one):		gent giv YES	en for ar	nticoagul NO	lation or antiplatelet therapy present durir
Reversal agent (check all that were given K centra Idarucizumab	en for re	versal o	of anticoa	agulatior 	n/antiplatelet therapy): Andexanet Vitamin K Other
Patient with coagulopathy present on a	dmissior	n? (Circ	le one):	YES	NO
Patient Initial INR:					
Initial Imaging/Injury Assessment					
Was an initial FAST performed? (Circle YES YES/positive	e one):	YES/r	negative		NO
Which area of the FAST was positive? Pericardial Right upper quadrant Left upper quadrant Suprapubic			apply):		
Was an initial CT scan performed? (Cir YES NO	cle one)		emergen	t OR	
Organs Injured (Circle one): LIVER SPLEEN		BOTH	I (Liver a	ind splee	en)
Grade of Liver (Circle one): 1	2	3	4	5	6
Grade of Spleen (Circle one): 1	2	3	4	5	
Repeat Imaging					
Was repeat imaging performed? (Circle	e one):	YES		NO	
If yes, CT or US? (Circle one):		СТ		US	
Time from initial presentation ir	hours:		_		
	ge (char Change	nge in p (instituti	onal rec	ommeno	dation, scheduled imaging)
Imaging Findings:					

Organ Specific Delayed Complications

Liver Complications (defined as complications found during hospital admission, check all that apply): Increased bleeding/increased hemoperitoneum Pseudoaneurysm

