	Both: Hepatic AND splenic injuries of any grade present on initial CT scan or found in OR at initial emergent operation.
Grade of Liver	Single choice for grade of hepatic injury following AAST grading scale. If no hepatic injury present, leave blank. Note: Advance one grade for multiple hepatic injuries up to grade 3. Options include:
	Grade 1: Subcapsular hematoma <10% surface area. Parenchymal laceration <1 cm in depth.
	Grade 2: Subcapsular hematoma 10-50% surface area; intraparenchymal hematoma <10 cm diameter. Laceration 1-3 cm depth and <10 cm length.
	Grade 3: Subcapsular hematoma >50% surface area; ruptured subcapsular or parenchymal hematoma. Intraparenchymal hematoma >10 cm. Laceration > 3 cm depth. Any injury in the presence of a liver vascular injury or active bleeding contained within liver parenchyma.
	Grade 4: Parenchymal disruption involving 25-75% of a hepatic lobe. Active bleeding extending beyond the liver parenchyma into the peritoneum.
	Grade 5: Parenchymal disruption >75% of hepatic lobe. Juxtahepatic venous injury to include retrohepatic vena cava and central major hepatic veins.
	Grade 6: Hepatic avulsion.
Grade of Spleen	Single choice for grade of splenic injury following AAST grading scale. If no splenic injury present, leave blank. Note: Advance one grade for multiple splenic injuries up to grade 3. Options include:
	Grade 1: Subcapsular hematoma <10% surface area. Parenchymal laceration <1 cm depth. Capsular tear.
	Grade 2: Subcapsular hematoma 10-50% surface area; intraparenchymal hematoma <5 cm. Parenchymal laceration 1-3 cm depth.
	Grade 3: Subcapsular hematoma >50% surface area; ruptured subcapsular or intraparenchymal hematoma ≥5 cm. Parenchymal laceration >3 cm depth.

	Grade 4: Any injury in the presence of a splenic vascular injury or active bleeding confined within the splenic capsule. Parenchymal laceration involving segmental or hilar vessels producing >25% devascularization.
	Grade 5: Any injury in the presence of splenic vascular injury with active bleeding extending beyond the spleen into the peritoneum.
Repeat Imaging	
First Repeat Imaging	Yes/No dropdown menu. Yes = Repeat abdominal imaging performed during same hospital admission. No = No additional abdominal imaging performed during same hospital admission.
First Repeat Imaging Type	If yes checked for First Repeat Imaging, single choice for type of repeat imaging. Options include: Computed Tomography (CT) Ultrasound (US)

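### Pseudoaneurysm and arteriovenous fistula can be ticked as delayed complications although already present on the initial CT, and the same lesion may also set the baseline injury grade

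*Supplement*

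**What the plan says.** The protocol gives the outcome as "Primary Outcome: Delayed complications found on repeat imaging". It sets no time threshold for delayed and no rule about what the initial scan must have shown.

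The fields that capture the outcome are in the data dictionary under Organ Specific Delayed Complications. For the spleen: "Spleen specific complications found during hospital admission. Check all that apply". For the liver: "Liver specific complications found during hospital admission. Check all that apply". The data collection tool agrees: "Liver Complications (defined as complications found during hospital admission, check all that apply". The repeat-imaging items just above are completed only if a repeat scan was done. The complication fields have no such condition.

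Some options in the lists do carry a condition, for example "New area of splenic injury not previously recognized on initial workup" and "Need for OR/intervention other than initial". Pseudoaneurysm (liver and spleen) and arteriovenous fistula (spleen only) are listed without one.

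The baseline grade is in the dictionary's Initial Imaging block. For the spleen: "Grade 4: Any injury in the presence of a splenic vascular injury or active bleeding confined within the splenic capsule". Grade 5 is a splenic vascular injury with bleeding into the peritoneum. For the liver, the grade 3 criteria include: "Any injury in the presence of a liver vascular injury or active bleeding contained within liver parenchyma".

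**The concern.** The outcome field covers the whole admission, and the baseline grade is read from the initial CT or first operation. For most options the wording or the nature of the event keeps the two apart. For pseudoaneurysm and arteriovenous fistula nothing does. One lesion can raise the grade on arrival and be ticked as a complication when the repeat scan shows it unchanged.

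Aim 1 is to define which injuries are at risk of delayed complications, with a management guideline in view, and the background wants low, moderate and high grades separated. If persisting lesions are counted as events, the extra events fall in the grades that vascular injury defines, so the error runs in one direction. The association with grade and the complication rate would both be too high, and part of what looks like new disease on re-imaging would have been visible on the first scan.

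**Working it through.** **Can one lesion enter both variables?** Take a spleen with a pseudoaneurysm on the initial CT that is still present, unchanged, on the repeat CT.

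- *Grade.* If a pseudoaneurysm counts as a splenic vascular injury, the grade is at least 4. The dictionary does not define vascular injury, so this is a reasonable reading but an inference.
- *Outcome.* The lesion is found during the admission and is visible on repeat imaging. The option has no newness condition, so ticking it agrees with the field's wording.
- *Separation afterwards.* No structured field records a vascular lesion on the initial CT. Grade cannot stand in for one, because spleen grade 4 and liver grade 3 also have parenchymal criteria. Noting which scan showed the lesion would not settle it, since a persisting lesion appears on both.

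**Size.** The documents contain no figure for this overlap, so there is no stated result to reproduce. The only anchors are the pilot complication rates among re-imaged patients (Sample Size and Power Estimates):

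- spleen: 46/105 = 0.438, stated as 0.44
- liver: 30/122 = 0.246, stated as 0.25

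Assumptions that are not in the documents:

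- The true rate p of new complications is the same in spleen grades 1-3 and 4-5, so the true odds ratio is 1.0.
- A share v of grade 4-5 patients has a baseline vascular lesion that is ticked as a complication, independently of any new one.
- Grades 1-3 gain no events this way, because a vascular lesion would have moved the patient to grade 4 or above.

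The range v = 0.15 to 0.30 corresponds to 30% of grade 4-5 spleens having such a lesion, with half (0.30 × 0.5 = 0.15) or all (0.30 × 1.0 = 0.30) of them ticked.

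Recorded rate in grades 4-5: q = 1 − (1 − p)(1 − v). Spurious odds ratio: [q/(1 − q)] / [p/(1 − p)].

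| p | v | q | Odds ratio |
|---|---|---|---|
| 0.44 | 0 | 0.44 | 1.0 |
| 0.44 | 0.15 | 1 − 0.56 × 0.85 = 0.524 | (0.524/0.476)/(0.44/0.56) = 1.40 |
| 0.44 | 0.30 | 1 − 0.56 × 0.70 = 0.608 | (0.608/0.392)/(0.44/0.56) = 1.97 |
| 0.25 | 0.15 | 1 − 0.75 × 0.85 = 0.3625 | (0.3625/0.6375)/(0.25/0.75) = 1.71 |
| 0.25 | 0.30 | 1 − 0.75 × 0.70 = 0.475 | (0.475/0.525)/(0.25/0.75) = 2.71 |

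The rate of 0.25 shows how the result depends on p. It matches the pilot liver figure; the pilot spleen figure is 0.44, so the first three rows are the ones anchored to the spleen.

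The complication rate in grades 4-5 rises by v(1 − p). At p = 0.44 that is 0.15 × 0.56 = 0.084 to 0.30 × 0.56 = 0.168. The rise in the overall rate is this amount times the share of patients in grades 4-5, which the documents do not give.

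**The case against.** The strongest reply is that context supplies what the field leaves out. The fields stand under a heading that says delayed and directly follow the repeat-imaging block, and the primary outcome says found on repeat imaging. Increased bleeding, delayed rupture, a newly recognised area of injury and a need for further intervention all imply change, and thrombosis is qualified as unexpected. A careful abstractor may well leave a persisting lesion unticked.

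This stands in part. A reader might infer that the fields accept any lesion found during the admission. The heading and these options do not support that. A reader might also extend the circularity to infarct, abscess or bile leak; the grading scale does not name these as criteria, so the overlap with grade is confined to vascular lesions. What the context does not do is say delayed relative to what. At 200 patients per site, 5,000 patients means 5,000/200 = 25 sites, each settling the question for itself.

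A second reply is that the cases could be found later. The findings of the first repeat scan and the description of the initial intervention are free text, and the timing of the initial intervention is recorded. So it would be too strong to say that the analyst cannot remove any of these cases. But none of these fields asks whether the lesion was there at baseline, so identification would be incomplete.

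Third, the sample size is set for the comparison of clinical-change with non-clinical-change imaging, and grade is not named as a model covariate. Both are correct. A reader might infer that the powered comparison is biased too, but that needs persisting lesions to be ticked more often in one group, and the documents give no evidence of it. The concern rests on Aim 1 and the intended separation by grade, for which grade is collected and is the natural predictor.

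**Conclusion.** The point holds for the pseudoaneurysm option in both organs and the arteriovenous fistula option in the spleen. As worded, a lesion present on the initial CT and persisting on the repeat scan can be recorded as a delayed complication. If vascular injury includes these lesions, the same finding also sets spleen grade 4-5 or liver grade 3. The field rule is thus broader than the primary outcome that it is meant to capture.

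The direction of the bias is upward for the grade-complication association and for the complication rate. Its size cannot be computed from the documents. With 15-30% of grade 4-5 spleens affected and no true association, the spurious odds ratio is about 1.4-2.0 at the pilot spleen rate, or 1.7-2.7 at a rate of 0.25. If abstractors tick no baseline lesions it is 1.0. These are illustrations and should not be read as estimates of the bias in this study.

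**What to change.** 1. In the liver and spleen complication definitions, state that a delayed complication is new, or worse, compared with the initial CT or initial operation, and that a lesion already present and unchanged is not ticked.
2. Add one Yes/No field per organ for a vascular injury (pseudoaneurysm, arteriovenous fistula, active bleeding) on the initial CT.
3. Prespecify a sensitivity analysis of the delayed-complication model that excludes patients with a baseline vascular lesion. Its result applies only to patients without such a lesion, so report it beside the main analysis.

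The cost is one sentence of definition and two REDCap fields. Sites already consult the initial CT to assign the grade, so the extra abstraction is small, although records already entered would have to be revisited. The headline complication rate may come out lower.
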